A repeated-SC dose study was intended to bridge to existing repeat IV dose nonclinical safety data. Cynomolgus monkeys received SC injections of control article or 10 or 100 mg/kg MEDI-545 weekly for 4 weeks for a total of 4 doses. Toxicity was assessed based on survival, clinical observations, body weight, physical examinations, dermal scoring, ophthalmic examinations, ECG examination, blood pressure, clinical pathology, organ weights, and macroscopic and microscopic pathology. All animals survived until their scheduled sacrifice. No adverse treatment-related findings occurred in any of the parameters assessed. The NOAEL for the repeated-dose SC toxicity study was determined to be at least 100 mg/kg, the highest dose tested. In tissue cross-reactivity studies, MEDI-545 did not bind to any of the human or cynomolgus monkey tissues tested.

Human type I IFNs include 13 subtypes of IFN- α , and there is no clear one-to-one correspondence between human IFN- α subtypes and those in other mammalian species. The specific roles of IFN- α subtypes in host defense against viral infections and in humans are unknown. Theoretically, blockade of most subtypes of IFN- α could potentially impair host responses to viral infections. Given the lack of direct correspondence between human and other mammalian IFN- α subtypes, animal models may not usefully predict the possible clinical effects of MEDI-545 in naturally occurring infections in patients with myositis. As such, the most appropriate way to evaluate effect of MEDI-545 on viral infections is by careful clinical monitoring in humans.

Further details of the preclinical information on MEDI-545 can be found in the investigator's brochure.

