A third study of MEDI-545 in patients with SLE (MI-CP179) will be evaluating the safety and tolerability of multiple SC dose schedules of MEDI-545 and/or placebo. In this study, a total of 80 patients will be randomized in a 1:1:2:2:2 ratio to receive 1 of 5 treatment arms of MEDI-545 or placebo as follows: (1) SC MEDI-545 100 mg once, SC Placebo \times 12 doses on other weeks;

(2) SC MEDI-545 100 mg every 4 weeks × 4 doses, SC Placebo × 9 doses on other weeks; (3) SC MEDI-545 100 mg every 2 weeks × 7 doses, SC Placebo × 6 doses on other weeks; (4) SC MEDI-545 100 mg every week × 13 doses, and (5) SC Placebo every week × 13 doses. As of [REDACTED], 74 patients have been dosed in MI-CP179. The majority of AEs are mild or moderate in severity. The most common AEs (incidence > 10%) are upper respiratory tract infection and nausea. There are no viral reactivation AEs. There was one case of breast cancer (angiosarcoma) that was judged by the investigator as being not related to study drug. There are no deaths reported in MI-CP179. Five of the 74 patients (6.8%) had SAEs. Two SAEs (cellulitis and pneumonia) were judged by the investigator as related to study drug.

As a fully human Mab, MEDI-545 is expected to have a safety profile similar to other agents in this class, including the potential for infusion reactions, injection-site reactions, fever, rashes, allergic reactions, bronchospasm, anaphylaxis, and serum sickness. In addition, potential reactions are expected to be related to the mechanism of action, the neutralization of most IFN- α subtypes, as well as the underlying patient population and treatments. IFN- α has a role in host defenses against viral infections. Patients at high risk for viral infections will be excluded from the current clinical study. Those enrolled in the study will be monitored clinically and through blood samples and cultures for viral infections.

Further details of the clinical information on MEDI-545 can be found in the investigator's brochure.

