3.1.2 Exclusion Criteria

Patients must have *none* of the following criteria:

1. Receipt of MEDI-545 in any previous clinical study or prior randomization into the trial;
2. History of allergy or reaction to any component of the study drug formulation;
3. Inclusion body myositis, cancer-associated myositis, myositis associated with another connective tissue disease, environmentally-associated myositis, or drug-related myopathy;
4. A history of or a family history of noninflammatory myopathy, scapular winging, atrophy, or hypertrophy of the calf muscles;
5. Receiving prednisone > 35 mg/day (or an equivalent dose of another corticosteroid) within 14 days before Study Day 0;
6. Receiving the following dosages of medications within 28 days before Study Day 0: hydroxychloroquine > 600 mg/day, mycophenolate mofetil > 3 g/day, methotrexate > 25 mg/week, azathioprine > 3 mg/kg/day, or any dose of cyclophosphamide, cyclosporine, or thalidomide;
7. Have received fluctuating doses of antimalarials, mycophenolate mofetil, methotrexate, leflunomide, or azathioprine within 28 days before Study Day 0 or fluctuating doses of corticosteroids within 14 days before Study Day 0;
8. Have received leflunomide > 20 mg/day in the 6 months prior to Study Day 0.
9. Treatment with any investigational drug therapy within 28 days before Study Day 0 or biologic therapies (eg, rituximab) within 30 days or 5 half-lives of the biologic agent, whichever is longer, before Study Day 0;
10. In the investigator's opinion, evidence of clinically significant active infection, including ongoing, chronic infection, within 28 days before Study Day 0;
11. A history of severe viral infection as judged by the investigators, including severe infections of either CMV or the herpes family such as disseminated herpes, herpes encephalitis, ophthalmic herpes;
12. Herpes zoster \leq 3 months prior to Study Day 0;
13. Evidence of infection with hepatitis B or C virus or HIV-1 or HIV-2, or active infection with hepatitis A, as determined by results of testing at screening;
14. Vaccination with live attenuated viruses within 28 days before Study Day 0;
15. Pregnancy (sexually active women, unless surgically sterile or at least 2 years post-menopausal, must have a negative serum pregnancy test at screening and a negative urine pregnancy test prior to study drug administration on Study Day 0);
16. Breastfeeding or lactating women;
17. History of alcohol or drug abuse < 1 year prior to Study Day 0;

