18. History of cancer, except for basal cell carcinoma or carcinoma in situ of the cervix treated with apparent success with curative therapy more than 1 year prior to Study Day 0;
19. History of active TB infection;
20. History of latent TB infection or newly positive TB skin test (reaction defined as \geq 10 mm in diameter if not on systemic immunosuppressive medication or \geq 5 mm if on systemic immunosuppressive medication) without completion of an appropriate course of treatment or ongoing prophylactic therapy;

21. A history of coagulation disorders that in the opinion of the investigator would contraindicate skin or muscle biopsies;
22. Elective surgery planned from the time of screening through Study Day 196;
23. At screening blood tests (must be within 28 days before Study Day 0) any of the following:
 - Serum creatinine > 4.0 mg/dL,
 - Neutrophils < 1,500/mm³,
 - Platelet count < 50,000/mm³;
24. History of any disease, evidence of any current disease (other than DM or PM), any finding upon physical examination, or any laboratory abnormality, that, in the opinion of the investigator or medical monitor, may compromise the safety of the patient in the study or confound the analysis of the study; or
25. Any employee of the research site who is involved with the conduct of the study.

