All patients should continue to receive medications they were taking at the time of consent in unchanged doses during the entire treatment; however, if clinical deterioration occurs and additional treatment is warranted in the opinion of the investigator, the investigator is permitted to add new or increase existing immunosuppressive medications, as long as no prohibited medications are added (see Section 3.4.5). Concurrent immunosuppressive therapy may be tapered and discontinued, according to the investigator’s judgment, during the follow-up period.

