3.4.4.2 Dose Modification for Toxicity Management: Blood Chemistry Abnormalities

If total bilirubin is $> 2 \times \text{ULN}$ at the central laboratory:

- Do not administer study drug at next dosing visit.
- Repeat total bilirubin as well as direct and indirect values, liver function tests (LFTs; including AST, ALT, and alkaline phosphatase), evaluate reticulocyte count immediately to confirm abnormalities. Repeat all tests again in 1 week.
 - If bilirubin remains $> 2 \times \text{ULN}$ (not due to Gilbert's syndrome or hemolysis) do not administer study drug at next dosing visit
 - If bilirubin returns to within normal limits ($< \text{ULN}$), study drug may be administered at next scheduled dosing visit
 - If repeat bilirubin is $< 2 \times \text{ULN}$ but $> \text{ULN}$; hold dose and discuss with medical monitor.

Study drug will be discontinued in subjects who miss 2 consecutive scheduled doses of study drug due to elevated bilirubin (see section 4.7).

If ALT or AST is $> 3 \times \text{ULN}$, refer to Guidance for Abnormal Liver Function Tests in Appendix J.

Study drug will be discontinued in subjects who miss 3 consecutive scheduled doses of study drug due to elevated ALT or AST (see 4.7).

As indicated in the Guidance for Abnormal Liver Function Tests (Appendix J), additional laboratory tests may be ordered from Quintiles Laboratory as needed. The LFTs that the guidelines require to be repeated are AST, ALT, total bilirubin and alkaline phosphatase.

Additional tests may be ordered as required by investigators, these tests include: CPK, GGT, INR, PT, albumin, EBV, CMV, hepatitis A antibody, hepatitis B surface antigen, hepatitis B core antibody and hepatitis C antibody.

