- b. If a patient discontinues after Study Day 196 and prior to Study Day 350, the evaluations scheduled for Study Day 350 must be completed. If a particular assessment has been performed within 2 weeks before the discontinuation visit, it need not be repeated.
- c. Vital signs include heart rate, blood pressure, respiratory rate and temperature.
- d. Includes Na, K, Cl, bicarbonate, BUN, creatinine, bilirubin, alkaline phosphate, and random glucose.
- e. At selected sites only.
- f. Serum muscle enzymes include CK, aldolase, AST, ALT, and LDH.
- g. Pulmonary function tests, a part of MDAAT, will assess lung volumes and DLCO.
- h. Physician Global Activity Assessment is included as part of MDAAT.
- i. Patient Global Activity Assessment is included as part of CLINHAQ.
- j. DM patients only.
- k. Optional procedures.
- l. Photographs of up to two target skin lesions (if present) are requested. One photograph should be of the skin lesion that was biopsied.
- m. Flow cytometry will be performed on peripheral blood samples from selected sites in North America.

Screening

Note: All screening laboratory assessments must be performed within 28 days before randomization (Study Day 0). The screening evaluations may be carried out over more than one visit. Chest x-ray taken within 6 months of screening is considered suitable for screening and need not be repeated.

1. Written informed consent
2. Verify eligibility criteria
3. Screening medical history
4. Chest x-ray
5. Screening physical examination
6. Screening ECG
7. TB skin test
8. Vital signs (temperature, blood pressure, pulse rate, respiratory rate)
9. Urinalysis
10. Blood collection for screening
 - Chemistry panel (including Na, K, Cl, bicarbonate, BUN, creatinine, bilirubin, alkaline phosphatase, and random glucose)
 - CBC with differential and platelet count
 - Serum for hepatitis A antibody, hepatitis B surface antigen, hepatitis C antibody and HIV-1 and HIV-2 antibodies
 - Serum β HCG (for women who are sexually active and are not surgically sterile or at least 2 years postmenopausal; this test must be negative for study participation)
 - Serum levels of muscle enzymes (including CK, aldolase, LDH, ALT, and AST)
 - Whole blood for IFN gene expression analysis
11. Disease activity assessments:
 - MMT for strength
 - Extramuscular activity assessment (based on MDAAT scales)
 - Pulmonary function tests
 - Physician global activity assessment (included as part of MDAAT)

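### Hepatitis B is screened by surface antigen alone, so the core antibody named for the on-study liver work-up has no scheduled pre-dose value

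*Protocol*

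**What the plan says.** Four parts of the protocol bear on the point.

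- **Screening tests (section 3.5, Screening).** The serology is "Serum for hepatitis A antibody, hepatitis B surface antigen, hepatitis C antibody and HIV-1 and HIV-2 antibodies". Table 4 lists hepatitis A, B and C without naming any further marker.
- **Eligibility (section 3.1.2).** Exclusion 13 bars "Evidence of infection with hepatitis B or C virus" or HIV, or "active infection with hepatitis A, as determined by results of testing at screening". Exclusion 24 allows exclusion for "any laboratory abnormality, that, in the opinion of the investigator or medical monitor, may compromise the safety of the patient".
- **On-study liver work-up (section 3.4.4.2).** Among the further tests investigators may order are "hepatitis A antibody, hepatitis B surface antigen, hepatitis B core antibody and hepatitis C antibody". Apart from the change log, this is the only place where core antibody appears.
- **Why viral status matters here.** Section 1.3 says that blocking most IFN-alpha subtypes "could potentially impair host responses to viral infections". Section 1.4 says "Patients at high risk for viral infections will be excluded from the current clinical study". Section 3.4.2 says "All patients should continue to receive medications they were taking at the time of consent in unchanged doses", and section 3.4.5 permits prednisone up to 35 mg/day and capped doses of methotrexate, azathioprine, mycophenolate and leflunomide.

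**The concern.** The protocol treats core antibody as informative once a liver signal has appeared, but never obtains it before the drug is given. Two things follow.

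First, an antigen-negative, core-antibody-positive patient without a known history passes screening unnoticed. The investigator and medical monitor have the discretion to act under exclusion 24, but not on a result nobody obtained.

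Second, if core antibody is ordered during a work-up and comes back positive, no scheduled result shows whether the finding predates the drug. Safety is the primary endpoint. Adverse events are summarized by relationship to study drug (section 5.4.1), and that judgement depends partly on whether another cause has been found (section 4.4). Under Table 1 every patient is due to receive MEDI-545 from Study Day 98 at the latest, so the question can arise for anyone enrolled.

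**Working it through.** The plan gives no figure on this point, so there is none to reproduce. The check compares the test lists and then counts.

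**1. Which scheduled procedure could show core-antibody status before dosing?**

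| Procedure | Source | Shows it? |
|---|---|---|
| Screening serology | 3.5 | No: surface antigen only for hepatitis B |
| Viral surveillance from Day 0 | Table 4 footnotes; 3.6.2 | No: EBV, CMV, HSV, HPV |
| ALT, AST, bilirubin | Table 4 | No: not serology |
| Medical history | Table 4, 3.5 | Only if the history is known |
| Optional stored Day 0 serum | Table 4, 3.6.7.1 | Not planned; could be tested later if kept |

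No scheduled test does.

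**2. Which work-up tests lack a scheduled pre-dose value?** Section 3.4.4.2 lists 11 additional tests.

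- With a scheduled value (6): CPK (measured as CK), EBV, CMV, hepatitis A antibody, hepatitis B surface antigen, hepatitis C antibody.
- Without (5): GGT, INR, PT, albumin, hepatitis B core antibody.

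That is 5 of 11, so core antibody is not unique. It is the only one of the five that bears on an infection named in exclusion 13.

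**3. Do the liver enzymes substitute for it?** Only weakly. Section 1.1 notes that the disease itself raises ALT and AST, and Appendix J admits patients above 2 × ULN at baseline. The Appendix J flow starts at 5 × ULN for patients at or below 2 × ULN at baseline. For the others it starts at a rise of 3 × ULN above their own baseline. In both, hepatitis testing is then something to consider, not a requirement.

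**4. How many patients can still benefit?**

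- Planned: 5 cohorts × 8 = 40 (section 5.2).
- Expansion: 5 × 4 = 20 at most (section 2.4.1).
- Maximum: 40 + 20 = 60.
- Dosed by 02/Nov/2009: 51 (section 1.5).
- Remaining: 60 − 51 = 9.

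The figure may be zero, because a cohort expands only if eligible patients are in screening when its eighth patient is randomized. Nor is 9 a hard ceiling, because replacements for nonevaluable patients are not counted.

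**5. Scale, on an assumption only.** The documents give no rate of antigen-negative, core-antibody-positive status. If the rate were p, the chance of at least one such patient among 9 would be 1 − (1 − p)^9:

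- p = 0.5%: 1 − 0.995^9 = 4.4%
- p = 3%: 1 − 0.97^9 = 24.0%
- p = 10%: 1 − 0.90^9 = 61.3%

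These are not estimates for this trial, and the conclusion does not rest on them.

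**The case against.** The strongest reply is that nothing in the protocol is broken, and most of that stands.

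- **Exclusion 13.** A reader might infer that the criterion is breached, or that core-antibody-positive patients are already barred because only hepatitis A is limited to active infection. The text does not support this. The criterion ties itself to the screening results, screening tests surface antigen, and nothing states that an isolated core antibody counts as infection.
- **Size of the hazard.** A reader might infer that such patients are at established risk of reactivation on this drug. The protocol does not say so. Its statement on antiviral responses is general and theoretical, and it points to clinical monitoring as the way to evaluate the effect.
- **Undetected.** This holds only for scheduled tests. Medical history, which covers viral reactivation events, is taken at screening and updated on Day 0. A known history can be acted on under exclusion 24.
- **No baseline.** This means no scheduled result. Stored pre-dose serum might be tested later, but storage is optional and no hepatitis B use is planned.
- **Existing monitoring.** ALT, AST and bilirubin are measured at every dosing visit. Appendix J withholds the drug at its thresholds, asks about hepatitis exposure and brings in the medical monitor, whatever the core-antibody status. Surface antigen has a pre-dose value, so that comparison is available.

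What the reply does not remove is the patient whose history is unknown, and the work-up result with no scheduled value before it.

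**Conclusion.** The point holds as a gap in screening and baseline data. It is not a contradiction or a breached rule. Surface antigen is the only scheduled hepatitis B marker, and the core antibody the protocol itself names for liver work-ups is not measured before dosing. What is affected is patient safety and the attribution of liver events. No dosing rule, endpoint definition or statistical figure changes.

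The size is small: about 0 to 9 patients still to be enrolled. This takes the 51 dosed at the November 2009 cut-off as current and leaves replacements out. The number who would test positive is unknown and may be none. The recommendation rests on the low cost of the test and the protocol's own concern about viral infection, not on a demonstrated risk. It is a cheap improvement.

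**What to change.** Add hepatitis B core antibody to the screening serology in section 3.5 for every patient still to be enrolled. Record it as a baseline, and state that the investigator and medical monitor weigh a positive result under exclusion 24. Whether a positive result should exclude outright is a clinical decision for the sponsor. If it should, exclusion 13 ought to say so. For patients already dosed, testing stored pre-dose serum is optional, subject to availability and consent.

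The cost is one assay on blood already drawn, at the central laboratory that already runs the hepatitis serologies (section 3.6.1). It also takes a protocol amendment with IRB/IEC approval before use (section 10), and possibly a few screen failures. No extra visit or procedure is needed.

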4. ECG
5. Urinalysis includes collection of urine for β HCG (for women who are sexually active and are not surgically sterile or at least 2 years postmenopausal)
6. Blood collection
 - Chemistry panel
 - CBC with differential and platelet count
 - Serum levels of muscle enzymes
 - Serum for exploratory research (including IFN- α assay and proteomics) and storage
 - Serum for autoantibodies (including ANA, anti-SSA, anti-RNP, anti-Jo-1, anti-SRP, anti-Mi-2 antibodies)
 - Whole blood for IFN gene expression analysis
 - Peripheral blood for flow cytometry
 - MEDI-545 serum level
 - Anti-MEDI-545 antibodies
7. Viral surveillance testing
8. Disease activity assessments:
 - MMT
 - Extramuscular activity assessment
 - Pulmonary function tests (within 7 days before the visit)
 - Physician global activity assessment (included as part of MDAAT)
 - CLINHAQ (includes Patient global activity assessment)
 - Myositis Damage Index
 - SF-36v2
 - WPAI: SHP questionnaire
 - Pruritus VAS (DM patients only)
 - CDASI (DM patients only)
 - DLQI (DM patients only)

9. Skin photographs (optional, DM patients only, preferably prior to the punch skin biopsy and within 7 days before the visit)
10. Muscle biopsy (within 7 days before the visit). Open muscle biopsy for IFN gene expression analysis
11. Punch skin biopsy (optional punch biopsy, DM patients only, within 7 days before the visit). Skin for IFN gene expression analysis
12. Vital signs before administration of study drug
13. Administration of study drug (Study Day 98 only)
14. AE/SAE assessment
15. Post-dose blood collection (within 10 minutes after the infusion has stopped and 2 hours after study drug administration)
 - MEDI-545 serum level
16. Monitor vital signs up to 30 minutes before dosing, approximately every 15 minutes during administration of the drug, immediately after the infusion (within 10 minutes after the infusion has stopped), and approximately every 30 minutes after the completion of the infusion until stable. Measure blood pressure and heart rate prior to discharge from the site.

Study Day 182 (\pm 1 Day): Treatment Period

Visit 14

1. Record concomitant medications
2. Urinalysis includes collection of urine for β HCG (for women who are sexually active and are not surgically sterile or at least 2 years postmenopausal)
3. Blood collection
 - Chemistry panel
 - CBC with differential and platelet count
 - Serum levels of muscle enzymes
 - MEDI-545 serum level
4. Vital signs up to 30 minutes before administration of study drug
5. Administration of study drug
6. Monitor vital signs approximately every 15 minutes during administration of the drug, immediately after the infusion (within 10 minutes after the infusion has stopped), and approximately every 30 minutes after the completion of the infusion until stable. Measure blood pressure and heart rate prior to discharge from the site.
7. AE/SAE assessment
8. Post-dose blood collection (within 10 minutes after the infusion has stopped and 2 hours after study drug administration)
 - MEDI-545 serum level

Study Days 185, 189 (\pm 1 Day): Follow-Up Period

Visits 15, 16

These visits must take place after the Study Day 182 visit.

1. Vital signs
2. AE/SAE assessment

3. Blood collection:
 - MEDI-545 serum level

Study Day 196 (± 3 Days): Follow-Up Period or Discontinuation Visit

If a patient discontinues the study prematurely after Study Day 98 and prior to Study Day 196, he or she should return to the study site and complete the following evaluations. If a particular assessment has been performed within 2 weeks before the discontinuation visit, it need not be repeated.

Visit 17

1. Record concomitant medications
2. Physical examination
